16.3 Appendix 3: MFSAF v4.0 PRO

Myelofibrosis Symptom Assessment Form version 4.0 7-Day Recall (MFSAF v4.0 7-Day Recall)

Instructions: The following questions refer to symptoms that you may experience as a result of your myelofibrosis. Please read through and complete the questions on the following screens. There are no right or wrong answers. Please select the answer that best applies to you.

1	40	m	•	

1.	During the pas	t 7 day	/s, hov	v sevei	re was	your v	vorst fa	atigue ((weari	ness, t	tiredness)?
	0	1	2	3	4	5	6	7	8	9	10
	Absent										Worst Imaginable
2.	During the pas	t 7 day	/s, hov	v sevei	re wer	e your	worst	night s	weats	(or fe	eling hot or flushed)?
	0	1	2	3	4	5	6	7	8	9	10
	Absent										Worst Imaginable
3.	During the pas	t 7 day	/s, hov	v sevei	re was	your v	vorst it	ching?			
	0	1	2	3	4	5	6	7	8	9	10
	Absent										Worst Imaginable
4.	During the past bloating)?	t 7 day	/s, hov	v sevei	re was	your v	vorst a	bdomi	nal dis	comfc	ort (feeling pressure o
	0	1	2	3	4	5	6	7	8	9	10
	Absent										Worst Imaginable
5.	During the pas	t 7 day	/s, hov	v sevei	re was	the wo	orst pa	in und	er you	r ribs (on your left side?
	0	1	2	3	4	5	6	7	8	9	10
	Absent										Worst Imaginable
6.	During the pas	t 7 day	/s, wha	at was	the wo	orst fee	eling of	f fullne	ss you	had a	fter beginning to eat?
	0	1	2	3	4	5	6	7	8	9	10
	Absent										Worst Imaginable
7.	During the pas	t 7 day	/s, hov	v sevei	re was	your v	vorst b	one pa	iin (no	t joint	or arthritis pain)?
	0	1	2	3	4	5	6	7	8	9	10
	Absent										Worst Imaginable

16.4 Appendix 4: EORTC QLQ-C30 PRO

ENGLISH

Very

Much

Quite

a Bit

Not at

All

 \mathbf{A}

Little

EORTC QLQ-C30 (version 3)

We are interested in some things about you and your health. Please answer all of the questions yourself by circling the number that best applies to you. There are no "right" or "wrong" answers. The information that you provide will remain strictly confidential.

Please fill in your initials:		L	\perp	L	\perp	╛				
Your birthdate (Day, Month, Year):		L	L	1		1	1	ı	1	J
Today's date (Day, Month, Year):	31	L	ı	1		L	1	1		J

Do you have any trouble doing strenuous activities, like carrying a heavy shopping bag or a suitcase?	1	2	3	4	
Do you have any trouble taking a long walk?	1	2	3	4	
Do you have any trouble taking a short walk outside of the house?	1	2	3	4	
Do you need to stay in bed or a chair during the day?	1	2	3	4	
Do you need help with eating, dressing, washing yourself or using the toilet?	1	2	3	4	
uring the past week:	Not at All	A Little	Quite a Bit	Very Much	
Were you limited in doing either your work or other daily activities?	1	2	3	4	
Were you limited in pursuing your hobbies or other leisure time activities?	1	2	3	4	
Were you short of breath?	1	2	3	4	
Have you had pain?	1	2	3	4	
Did you need to rest?	1	2	3	4	
Have you had trouble sleeping?	1	2	3	4	
Have you felt weak?	1	2	3	4	
Have you lacked appetite?	1	2	3	4	
Have you felt nauseated?	1	2	3	4	
Have you vomited?	1	2	3	4	
	Do you have any trouble taking a long walk? Do you have any trouble taking a short walk outside of the house? Do you need to stay in bed or a chair during the day? Do you need help with eating, dressing, washing yourself or using the toilet? uring the past week: Were you limited in doing either your work or other daily activities? Were you limited in pursuing your hobbies or other leisure time activities? Were you short of breath? Have you had pain?	like carrying a heavy shopping bag or a suitcase? Do you have any trouble taking a long walk? Do you have any trouble taking a short walk outside of the house? Do you need to stay in bed or a chair during the day? Do you need help with eating, dressing, washing yourself or using the toilet? It is the past week: Were you limited in doing either your work or other daily activities? Were you limited in pursuing your hobbies or other leisure time activities? Were you short of breath? Have you had pain? Did you need to rest? Have you had trouble sleeping? Have you lacked appetite? 1 Have you lacked appetite?	like carrying a heavy shopping bag or a suitcase? Do you have any trouble taking a long walk? Do you have any trouble taking a short walk outside of the house? Do you need to stay in bed or a chair during the day? Do you need help with eating, dressing, washing yourself or using the toilet? In the past week: Not at All Little Were you limited in doing either your work or other daily activities? Were you limited in pursuing your hobbies or other leisure time activities? Have you had pain? Did you need to rest? Have you had trouble sleeping? Have you lacked appetite? 1 2 Have you lacked appetite? 1 2 Have you lacked appetite?	like carrying a heavy shopping bag or a suitcase? 1 2 3 Do you have any trouble taking a long walk? 1 2 3 Do you have any trouble taking a short walk outside of the house? 1 2 3 Do you need to stay in bed or a chair during the day? 1 2 3 Do you need help with eating, dressing, washing yourself or using the toilet? 1 2 3 Writing the past week: Not at All Little a Bit Were you limited in doing either your work or other daily activities? 1 2 3 Were you limited in pursuing your hobbies or other leisure time activities? 1 2 3 Were you short of breath? 1 2 3 Have you had pain? 1 2 3 Have you felt weak? 1 2 3 Have you felt weak? 1 2 3 Have you felt nauseated? 1 2 3 Have you felt nauseated?	like carrying a heavy shopping bag or a suitcase? 1 2 3 4 Do you have any trouble taking a long walk? 1 2 3 4 Do you have any trouble taking a short walk outside of the house? 1 2 3 4 Do you need to stay in bed or a chair during the day? 1 2 3 4 Do you need help with eating, dressing, washing yourself or using the toilet? 1 2 3 4 In the past week: Not at All Little a Bit Much Were you limited in doing either your work or other daily activities? 1 2 3 4 Were you limited in pursuing your hobbies or other leisure time activities? 1 2 3 4 Were you short of breath? Have you had pain? 1 2 3 4 Have you had trouble sleeping? 1 2 3 4 Have you lacked appetite?

Please go on to the next page

ENGLISH

During the past week:	Not at All	A Little	Quite a Bit	Very Much
17. Have you had diarrhea?	1	2	3	4
18. Were you tired?	1	2	3	4
19. Did pain interfere with your daily activities?	1	2	3	4
20. Have you had difficulty in concentrating on things, like reading a newspaper or watching television?	1	2	3	4
21. Did you feel tense?	1	2	3	4
22. Did you worry?	1	2	3	4
23. Did you feel irritable?	1	2	3	4
24. Did you feel depressed?	1	2	3	4
25. Have you had difficulty remembering things?	1	2	3	4
26. Has your physical condition or medical treatment interfered with your family life?	1	2	3	4
27. Has your physical condition or medical treatment interfered with your social activities?	1	2	3	4
28. Has your physical condition or medical treatment caused you financial difficulties?	1	2	3	4

[figure not shown]
For the following questions please circle the number between 1 and 7 that best applies to you

29.	How wo	uld you rate	e your overa	ll health dur	ring the past	week?	
	1	2	3	4	5	6	7
Ver	y poor						Excellent
30.	How wo	uld you rate	e your overa	ll quality of	life during	the past wee	k?
	1	2	3	4	5	6	7
Ver	y poor						Excellent

16.6 Appendix 6: Statistical considerations for dose-escalation

This appendix provides details of the statistical model, the derivation of prior distributions from historical data, the results of the Bayesian analyses and respective dosing decisions for some hypothetical data scenarios, and a simulation study of the operating characteristics of the model.

16.6.2 Statistical model

Let $\pi(d)$ be the risk of DLT for the combination of ruxolitinib given at dose combination agent (siremadlin or rineterkib) dose d, the dose-DLT model is logistic:

Figure 16-1 Logistic DLT model.

$$logit(\pi(d)) = log(\alpha) + \beta log(d/d^*)$$

where d* is used to scale the doses. Hence, $\alpha > 0$ is the odds of a DLT at d*; and $\beta > 0$ is the increase in the log-odds of a DLT by a unit increase in log-dose.

16.6.3 Prior specifications for logistic parameters

The Bayesian approach requires the specification of prior distributions for the model parameters $log(\alpha)$ and $log(\beta)$. A meta-analytic-predictive (MAP) approach was used to derive the prior distribution for these model parameters.

16.6.3.1 Description of the meta-analytic-predictive (MAP) approach

The aim of the MAP approach is to derive a prior distribution for the logistic parameters $(\log(\alpha^*), \log(\beta^*))$ of the new trial using DLT data from historical studies.

Let r_{ds} and r_{ds} be the number of patients with a DLT, and the total number of patients at dose d in historical trial s (s = 1,...,S). The corresponding probability of a DLT is π_{ds} . The model specifications for the derivation of the MAP prior are as follows:

$$r_{ds} \mid \pi_{ds} \sim \text{Bin}(\pi_{ds}, n_{ds})$$

$$\log \text{It}(\pi_{ds}) = \log(\alpha_s) + \beta_s \log(d/d^*)$$

$$\left(\log(\alpha_s), \log(\beta_s)\right) \mid \mu, \psi \sim \text{BVN}(\mu, \psi), \quad s = 1, ..., S$$

$$\left(\log(\alpha^*), \log(\beta^*)\right) \mid \mu, \psi \sim \text{BVN}(\mu, \psi)$$

The parameters $\mu=(\mu_1,\mu_2)$ and ψ are the mean and between-trial covariance matrix for the logistic parameters, the latter with standard deviations τ_1 , τ_2 , and correlation ρ . The parameters τ_1 and τ_2 quantify the degree of between trial heterogeneity. The following priors will be used for these parameters:

- normal priors for μ₁ and μ₂,
- log-normal priors for τ_1 and τ_2 , and
- a uniform prior for ρ.

The MAP prior for single-agent model parameters in the new trial, $(log(\alpha^*), log(\beta^*))$, is the predictive distribution

$$\left(\log(\alpha^*),\log(\beta^*)\right)\big|\;(r_{ds},n_{ds}:s=1,\ldots,s)$$

Since the predictive distribution is not available analytically, MCMC is used to simulate values from this distribution. This is implemented using JAGS version 4.2.0. The sample from this distribution is then approximated by a mixture of bivariate normal (BVN) distributions. BVN mixtures with increasing numbers of mixture components are fitted to the sample using the expectation-maximization (EM) algorithm (Dempster et al 1977). The optimal number of components of the mixture is then identified using the Akaike information criterion (AIC) (Akaike H 1974).

16.6.3.2 Single-agent siremadlin

For the MAP model for siremadlin, reference dose $d^* = 50$ mg is used, and data from one historical study with four regimens is available, so S = 4 is chosen.

Weakly informative normal priors are assumed for μ_1 and μ_2 , with means corresponding to a risk of DLT at the reference dose of 1/3, and a doubling in dose leading to a doubling in the odds of the risk of a DLT, respectively. Priors for τ_1 and τ_2 are assigned such that (1) their medians correspond to substantial between trial heterogeneity, and (2) their uncertainty (95% prior interval) cover plausible between-trial standard deviations (Neuenschwander et al 2014).

The prior distributions for the model used for deriving the MAP priors are specified in Table 16-3.

Table 16-3 Prior distributions for the parameters of the MAP model used to derive the prior for the single-agent model parameters

Parameter	Prior Distribution
μ1	N (mean = logit (1/3), sd = 2)
μ_2	N (mean = 0, sd = 1)
t1	log-normal (mean = log (0.5), sd = log (2)/1.96)
t2	log-normal (mean = log (0.25), sd = log (2)/1.96)
ρ	uniform (-1,1)

Historical data from study CHDM201X2101

The prior is determined based on solid tumor data from study CHDM201X2101.

In this study, four different regimens and dose-schedules where studied:

- 1A: dose on day 1 of a three week cycle
- 1B: dose on day 1 and on day 8 of a four week cycle
- 2A: once dose daily for the first two weeks of a four week cycle
- 2C: once daily dosing for the first week of a four week cycle

The doses in the difference regimens are scaled to fit the schedule of siremadlin in the combination study, which is once daily for the first five days in a four-week cycle.

In study CHDM201X2101, the original interest was in DLTs in cycle 1, however after observing cumulative toxicity DLTs within the first two cycles were considered for the recommended dose for expansion (document release date 28-Oct-2016). As the ruxolitinib combination study focuses on DLTs occurring in the first two cycles, the corresponding DLTs from the study CHDM201X2101 were considered. When building the MAP prior distribution for siremadlin, the different regimens from study CHDM201X2101 were considered as different studies.

Table 16-4 Regimens and doses from study CHDM201X2101

Regimen	Dose level	Dose per cycle	Dose per day in 5 day schedule	N	DLTs (Cycle 1)	HEM DLTs (Cycle 2)	DLTs considered for MAP
1A	12.5	12.5	2.5	1	0	0	0
	25	25	5.0	1	0	0	0
	50	50	10.0	4	0	1	1
	100	100	20.0	4	0	0	0
	200	200	40.0	5	0	1	1
	250	250	50.0	6	0	1	1
	350	350	70.0	5	2	2	4
1B	120	240	48.0	9	0	2	2
	150	300	60.0	8	1	1	2
	200	400	80.0	3	0	Data n/a at cutoff	0
2A	1	14	2.8	1	0	0	0
	2	28	5.6	2	0	0	0
	4	56	11.2	4	0	0	0
	7.5	105	21.0	4	0	0	0
	15	210	42.0	4	0	1	1
	20	280	56.0	5	0	4	4
2C	15	105	21.0	8	0	1	1
	20	140	28.0	6	0	0	0
	25	175	35.0	5	2	0	2

Summary of prior distributions for siremadlin

To obtain the MAP prior for $(\log(\alpha), \log(\beta))$, the predictive distribution obtained from data in Table 16-4 will be mixed with a vague prior assuming a weight of 0.5. This mixing takes into account the fact the that patient population from study CHDM201X2101 and this combination study are not identical and that in this combination study a single-agent model is used to account for both the effect of siremadlin and potential interaction with ruxolitinib.

The MAP prior for $(\log(\alpha), \log(\beta))$ is a mixture of three multivariate normal distributions and it is summarized in Table 16-5.

Table 16-5 Prior distribution for the siremadlin model parameters

Prior for $(log(\alpha), log(\beta))$ in the single agent DLT-model for the combination of siremadlin and ruxolitinib						
	Mean	Standard Deviations	Correlation	Weight		
MAP component 1	(-0.771 ,0.492)	(0.700, 0.435)	0.221	0.3255		
MAP component 2	(-0.884, 0.051)	(0.573, 0.643)	0.237	0.1745		
MAP component 3	(logit(1/3), 0)	(2, 1)	0	0.5		
Prior summaries for [DLT rates for are sum	nmarized in Table 16-6	5.			

Summary of prior distribution of DLT rates for the combination of **Table 16-6** siremadlin and ruxolitinib

Siremadlin Dose (mg)	Prior Probabilities that P(DLT) is in the interval:			Mean	SD	Quantiles	3	
	(0, 0.16)	(0.16, 0.33)	[0.33,1]			2.5%	50%	97.5%
10	0.7982	0.0967	0.1051	0.1191	0.1895	0.0001	0.0443	0.7679
20	0.6526	0.1932	0.1542	0.1793	0.2103	0.0011	0.1046	0.8384
30	0.4687	0.3077	0.2235	0.2392	0.2217	0.0050	0.1713	0.8792
40	0.3035	0.3630	0.3335	0.2996	0.2297	0.0110	0.2425	0.9087

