12.4.2 Statistical model, hypothesis, and method of analysis

12.4.2.1 Part 1

Identification of a recommended dose for siremadlin and rineterkib

Identification of the RP2D of the combination treatment will be based upon the estimation of the probability of DLT within the first two cycles for patients in the DDS. A recommended dose below the MTD may be identified based on other safety, clinical, PK, and PD data (Section 6.5.2). The dose escalation will be guided by a Bayesian analysis of dose-limiting toxicity (DLT) data from Cycle 1 and Cycle 2. The relationship between dose and the probability of DLT is modelled using logistic regression. Details of the model are given in Section 16.6.

Assessment of patient risk

After each cohort of patients that have been followed for two cycles, the BLRM will be updated and the posterior distribution for the risk of DLTs for patients at dose levels of siremadlin of interest will be evaluated. The posterior distributions will be summarized to provide the posterior probability that the risk of a DLT within the first two cycles lies within the following intervals:

Table 12-1 Toxicity levels

Under-dosing:	[0, 0.16)
Targeted toxicity:	[0.16, 0.33)
Excessive toxicity:	[0.33 , 1]

The escalation with overdose control (EWOC) principle

Dosing decisions are guided by the escalation with overdose control principal. A dose of the combination agent may only be used for newly enrolled patients if the risk of excessive toxicity at that dose is less than 25%.

Prior distributions

A meta-analytic-predictive (MAP) approach was used to derive the prior distribution for the model parameters. The MAP prior for the logistic model parameters for this study is the conditional distribution of the parameters given the historical Neuenschwander et al 2014, Neuenschwander et al 2010, Spiegelhalter et al 2004). MAP priors are derived from hierarchical models, which take into account possible differences between the studies.

A full description of the application of the MAP approach to derive the prior distributions of the model parameters is given in Section 16.6.

Starting dose

The starting dose for siremadlin in combination with ruxolitinib is 20 mg (Section 6.5.1.1). For this dose the prior risk of excessive toxicity is 15.42% (see Section 16.6), which satisfies the EWOC criterion. Any dose lower than 20 mg also fulfills the EWOC criterion. A full assessment of the prior risk to patients is given in Section 16.6.

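### The two-cycle siremadlin prior counts three subjects at the highest historical dose as DLT-free although their Cycle 2 data were missing, which modestly understates toxicity at the upper doses

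*Protocol*

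**What the plan says.** Protocol Section 16.6.3.2 sets the window for the historical data: "As the ruxolitinib combination study focuses on DLTs occurring in the first two cycles, the corresponding DLTs from the study CHDM201X2101 were considered". Table 16-4 then lists DLTs by regimen and dose, with separate columns for Cycle 1, for Cycle 2 (headed "HEM DLTs (Cycle 2") and for the count passed to the MAP model. For regimen 1B at 200 mg the row reads N = 3, no Cycle 1 DLTs, "Data n/a at cutoff" for Cycle 2, and 0 DLTs considered. SAP Table 5-4 repeats the row. Neither document explains the zero.

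The likelihood in Protocol Section 16.6.3.1 is a plain binomial on DLTs and subjects. The overdose rule in Protocol Section 12.4.2.1 is that any siremadlin level "may only be used for newly enrolled patients if the risk of excessive toxicity at that dose is less than 25" per cent, where excessive toxicity means a DLT risk of 0.33 or more.

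**The concern.** A subject with no Cycle 2 data has not been shown to be free of a two-cycle DLT. Entering the row as 0/3 turns missing follow-up into three non-events at the dose with the most leverage on the slope. Three places in the documents make this hard to defend:

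- The source study moved to a two-cycle window because toxicity accumulated (Section 16.6.3.2).
- This trial's own Dose-Determining Set rule (Section 12.1.3) accepts a subject as DLT-free only if observed to the end of Cycle 2.
- For rineterkib, Section 16.6.3.3 justifies the use of one-cycle data by a review of second-cycle adverse events. Siremadlin has no such statement.

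At stake is the siremadlin DLT-risk posterior, on which the Part 1 RP2D statement partly rests. That objective is still in force (SAP Table 1-1).

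**Working it through.** **Where the DLTs fall.** From Table 16-4, Cycle 1: 2 (1A 350 mg) + 1 (1B 150 mg) + 2 (2C 25 mg) = 5. Cycle 2: 5 (1A) + 3 (1B) + 5 (2A) + 1 (2C) = 14. Total 19, which matches the MAP column. The next-highest scaled dose, 70 mg/day, had 4 DLTs in 5 subjects.

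**Model.** logit(pi) = log(alpha) + beta x log(d/50), since "reference dose $d^* = 50$ mg is used". The regimens are treated as separate studies ("data from one historical study with four regimens is available, so S = 4 is chosen"). Hyperpriors are those of Table 16-3. The predictive distribution is mixed 50:50 with a vague component, mean (logit(1/3), 0) and SD (2, 1), as in Protocol Table 16-5. SAP Table 5-5 prints logit(1/2) instead. That value gives 0.152/0.213/0.289/0.401 and does not reproduce the shared prior summary, so the protocol value is used here.

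**Reproducing the plan.** Integrating the printed Table 16-5 mixture gives P(DLT risk >= 0.33) of 0.106/0.157/0.226/0.334 at 10/20/30/40 mg, against 0.1051/0.1542/0.2235/0.3335 in Table 16-6. The nine Table 16-11 values reproduce within about 0.006; scenario 7 comes out at 0.247, as printed.

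**Was the row used as 0/3?** The two informative printed components average:

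- log alpha: (0.3255 x -0.771 + 0.1745 x -0.884)/0.5 = -0.81
- log beta: (0.3255 x 0.492 + 0.1745 x 0.051)/0.5 = 0.34

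Refitting by MCMC to Table 16-4 gives these means for (log alpha, log beta):

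| Treatment of the row | log alpha | log beta |
|---|---|---|
| Kept as 0/3 | -0.81 | 0.33 |
| Cycle 1 information only, 5/19 of DLTs assumed in Cycle 1 | -0.70 | 0.48 |
| Dropped | -0.68 | 0.51 |

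Only the first matches the printed prior.

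**Effect on prior P(excessive toxicity).** The last column shows the range if 1, 2 or 3 of the three had a Cycle 2 DLT.

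| Dose | Kept | Dropped | If 1/3, 2/3, 3/3 |
|---|---|---|---|
| 10 mg | 0.108 | 0.107 | not computed |
| 20 mg | 0.158 | 0.157 | 0.157, 0.157, 0.155 |
| 30 mg | 0.222 | 0.223 | 0.224, 0.224, 0.223 |
| 40 mg | 0.328 | 0.345 | 0.340, 0.352, 0.362 |

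**Effect on Table 16-11.**

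| Scenario (dose) | Printed | Kept | Dropped |
|---|---|---|---|
| 1 (40 mg) | 0.122 | 0.118 | 0.134 |
| 2 (30 mg) | 0.148 | 0.144 | 0.151 |
| 3 (20 mg) | 0.219 | 0.223 | 0.231 |
| 4 (30 mg) | 0.222 | 0.214 | 0.229 |
| 5 (30 mg) | 0.183 | 0.178 | 0.191 |
| 6 (30 mg) | 0.159 | 0.149 | 0.160 |
| 7 (20 mg) | 0.247 | 0.245 to 0.257 | 0.252 to 0.265 |

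Scenarios 8 and 9 stay far above the limit. The ranges for scenario 7 come from two mixture fits to the same model.

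**A case that does cross.** With 1/6 at 20 mg and 1/6 at 30 mg, P(excessive) at 40 mg is 0.237 under the printed prior and 0.224 to 0.225 in direct refits with the row kept. It is 0.258 to 0.260 with the row dropped and 0.253 with it as Cycle 1 information only.

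**How often.** Over 217 hypothetical data sets, the highest dose under the limit changed in 9 or 11, depending on the fit. Most changes were from 40 to 30 mg. In one fit, two went the other way.

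**The case against.** The strongest reply is that this changes little. No prior verdict moves, and 40 mg is already above 25% before any data. Eight of the nine Table 16-11 verdicts hold, even if all three subjects had a Cycle 2 DLT (scenario 4 then reaches 0.248). Half the prior weight is vague, and under Section 6.5.2 the model only guides decisions taken on all the data. Recruitment stopped on 17 June 2022, so no new subject will be dosed under the rule. Replacing the prior now would substitute a post hoc one for the prior that guided escalation. All of this stands. It limits the size of the point and shapes the remedy, but does not justify the zero.

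A reader might infer more than the documents support:

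- **That the model understates toxicity at every dose.** At 20 mg the mean DLT risk falls slightly when the row is dropped (0.180 to 0.176), because the slope steepens.
- **That scenario 7 is a decision reversed by the row.** With the row kept, its value already ranges from 0.245 to 0.257, so it sits on the limit either way.
- **That Cycle 2 non-haematologic DLTs were left out.** The column heading raises the question, since Table 6-4 counts such events, but neither document says whether any occurred.

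**Conclusion.** The coding is unsupported, and the printed prior contains it. Its effect is a flatter dose-DLT slope and a modest understatement of risk at the upper doses: about 0.33 against 0.34 a priori at 40 mg, and 0.22 to 0.24 against about 0.26 after 1/6 at 20 mg and 1/6 at 30 mg. That second example is a constructed outcome, not a protocol scenario, but it crosses the limit by more than the fits differ from one another.

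The documents do not support the broader claim that the overdose rule generally admitted doses it would otherwise have excluded. The three subjects' true Cycle 2 outcomes are unknown, and the changes in eligible dose are few and close to the limit. The figures rest on the protocol's vague component, on Table 16-4 as printed and, for the Cycle 1 version, on 5/19 of DLTs falling in Cycle 1. What remains affected is the reported siremadlin DLT posterior and the RP2D statement.

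**What to change.** Re-derive the siremadlin MAP prior with the regimen 1B 200 mg row removed, or entered as Cycle 1 information only with the assumed Cycle 1 share stated. Report the final siremadlin DLT posterior and RP2D statement under this prior beside the one that guided escalation; do not overwrite the latter. Supply corrected versions of Protocol Tables 16-5, 16-6 and 16-11 and SAP Tables 5-5, 5-6 and 5-11, and reconcile the vague component between the two documents at the same time. State whether any non-haematologic Cycle 2 DLTs occurred in the source study and, if so, include them.

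The cost is one MCMC rerun, a query to the source study and table updates. Overdose probabilities at the upper doses become slightly less favourable.
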